SS will be randomized to one of 3 conditions for a 5-week period: (1) VAR plus a mobile CM intervention, (2) VAR plus a non-contingent reinforcement (NR) control condition, and (3) PLA plus the NR condition. During the first week, participants will undergo a standard 7-day medication (VAR or PLA) dose run-up period and will receive voucher-based reinforcement for texting videos of themselves providing CO samples twice per day, regardless of CO level. In Weeks 2-5, participants will continue to text video samples twice per day and will receive voucher reinforcement that is either contingent upon abstinence, or contingent only upon submitting the video (NR). Participants will visit the laboratory each week to complete assessments of smoking, craving, withdrawal symptoms, mood, subjective effects of smoking and psychiatric symptoms. They will also complete the CPT, cognitive battery, measures of quit interest, and provide a saliva sample for cotinine analysis at the beginning and end of the intervention period. At the end of the intervention, participants will be provided with brief advice to quit smoking and will be offered referrals to community treatments. They will also be administered a debriefing questionnaire in which they are asked to guess their medication condition and asked about the intervention acceptability, their willingness to participate in longer CM trials, and their willingness to receive prize-based incentives rather than vouchers.

Two weeks after Session 6, participants will be contacted by phone and asked about the frequency and quantity of cigarette and other nicotine/tobacco product use since the end of the active treatment period. Those indicating that they have been abstinent in the last 7 days will be provided with taxi transportation and compensation to provide CO verification of abstinence. Participants will be asked whether they have contacted and attended any community cessation treatments, and about their current interest in treatment. Participants will again be offered referrals to cessation treatments in the community. This assessment, including CO verification of abstinence, will be repeated 2 weeks later.

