Following intent-to-treat principles, all randomized participants will be included in analyses. Baseline characteristics of the groups will be compared using ANOVAs for continuous variables and chi-square tests for categorical variables. CO levels from participants' videos will be averaged to provide a single CO measure for each week. Effects of the treatment groups on dependent measures (CO, total and consecutive abstinent CO samples, cigarettes per day, cotinine, QSU, MNWS, mood, CEQ, Stage of Change, Contemplation Ladder, cognitive scores (baseline co-varied), BPRS, Calgary Scale, AIMS, Simpson-Angus and BARS scores), will be analyzed with generalized linear mixed models (GLMMs) with Group (VAR + CM, VAR + NR, PLA + NR) as the between-subjects factor and Session as the within-subjects factor. We will examine main effects and the Group x Session interaction. This approach controls for correlations from repeated measurements and for person-level covariates. Baseline data will be imputed for missing. Differences will be considered significant when $p \leq .05$ and effect sizes will be calculated (Cohen, 1988). We will examine whether gender and FTND score (≤ 5 vs. ≥ 6) moderate treatment effects by adding these factors (separately) to each model. To examine whether reductions in smoking are mediated by changes in proposed targets, once the Group x Session GLMMs have been conducted, we will add concurrent QSU, MNWS and CEQ Reward and Satisfaction scores as covariates in these models to see the extent to which

smoking outcomes are attenuated by the mediators. We will use the same procedure to explore whether cognitive performance mediates smoking outcomes.

Feasibility outcomes include: median number of sessions attended, percentage of video samples submitted and percentage of those who indicate that they would be willing to participate in a longer CM trial. Responses to open-ended questions on the debriefing questionnaire will be described. Number and type of serious adverse events are expected to be rare so will be reported descriptively. Adverse event ratings will be analyzed individually using one maximum value over the 5 weeks for each person for each expected effect, including the baseline value of each item.

Quality Assurance

Procedures in place to ensure the validity and integrity of the data

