- 2) **Breach of Confidentiality**: The risk of the interview is loss of privacy if other people find out the results. We will work to ensure that the participant's confidentiality is kept, and a Certificate of Confidentiality will be obtained from NIDA to further protect confidentiality. Study data will be identified only by numeric code and stored in locked file cabinets, or on password-protected computers. A master list of participant names and contact numbers will be kept completely separate from other information about participants in order to facilitate study visit scheduling and coordination. Only those with a need to know (for assessments of adverse events) or mandated auditors will have access to the master list linking names and code numbers. Clinically important assessment data such as new concomitant medications or adverse events will be made available to the medical monitor so that he can evaluate the participant coordinate an effective response. All study staff have received (and new staff will receive) mandatory human subjects' protections training. All are highly experienced with relevant ethical principles, particularly around confidentiality. Digital video files of CO samples will be deleted once these data have been coded.
- 3) **Coercion**: Coercion can arise from the payments that participants can earn for participation. Payments are considered compensation for assessment and travel time, and the rate is consistent with local standards for research. The R21 study includes high-value cash incentives for abstinence, which is necessary for experimentally-controlling smoking abstinence in this study as we demonstrated in a previous study (Tidey et al., 2014). Participants are free to discontinue at any time and will receive compensation for the sessions that they complete at the same rate and in the same form as those who complete that study. As an added protection for participants, those who initiate and maintain abstinence in this study through Thursday and wish to remain abstinent can opt out of the post-abstinence smoking assessment and still receive full compensation, as long as they attend the visit for the same amount of time as those who smoke and complete the other assessments. The R33 study includes a contingency management (CM) system, in which participants will receive voucher-based incentives for abstinence. Incentive values are in line with those offered in other CM studies for smoking cessation (e.g., Dallery et al., 2013).

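### R33 weekly mean CO can favour VAR + mCM over the NR arms if smoking samples go unsent, because the plan does not say how an unsent video enters the weekly mean

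*Combined protocol and SAP*

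**What the plan says.** The R33 description (Summary of the Protocol) sets the payment rules. In Week 1 every arm receives "voucher-based reinforcement for texting videos of themselves providing CO samples twice per day, regardless of CO level". After that, "In Weeks 2-5, participants will continue to text video samples twice per day", and what is paid for differs by arm: participants "will receive voucher reinforcement that is either contingent upon abstinence, or contingent only upon submitting the video (NR"). The Coercion item under Potential risks of participation agrees, saying of the contingency management system that "participants will receive voucher-based incentives for abstinence". Neither place mentions a payment to a VAR + mCM participant for a sample that shows smoking.

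The Data Analysis Plan, R33 phase, defines the endpoint: "CO levels from participants' videos will be averaged to provide a single CO measure for each week". The repeated-measures model uses Session as the within-subjects factor. Missing data get one sentence: "Baseline data will be imputed for missing". It does not say whether the unit is the video, the week or the session.

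The same section also analyses "total and consecutive abstinent CO samples", cigarettes per day and cotinine. The video submission rate is listed only as a feasibility outcome, with no breakdown by arm.

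**The concern.** From Week 2 on, a participant in an NR arm who has smoked is still paid for the video, and a participant in the VAR + mCM arm is not. The incentive to send a sample therefore depends on both the arm and the CO value. A mean over the videos that arrive drops high values more readily in one arm than in the others. If the imputation sentence is applied after averaging, a week with even one video counts as observed, and the unsent samples inside it are never replaced.

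The R33 phase is not powered for group differences. Its stated purpose, apart from feasibility, is to give effect sizes that decide whether a larger trial is warranted (Power Calculation and Sample Size). A bias towards the experimental arm would enter that decision. It would also enter the mediation models, which take the smoking outcomes as their starting point.

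**Working it through.** **The plan's own figures.** The only computable R33 figure is enrolment: 48 / (1 - 0.20) = 60, as stated, giving 48 / 3 = 16 per arm with equal allocation. The plan gives no expected CO, submission rate or abstinence rate. The schedule is 2 videos a day, so 2 x 7 = 14 a week and 14 x 4 = 56 over Weeks 2-5.

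**Assumptions (none from the documents).** Smoking samples 18 ppm, abstinent samples 3 ppm, baseline 20 ppm (also 25 and 30). The share of samples that show smoking, p, is 0.4, 0.6 or 0.8 and is *the same in both arms*. NR sends 80% of all samples. VAR + mCM (CM below) sends 85% of abstinent samples and a fraction s of smoking samples.

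**Step 1, mean of submitted videos.**

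NR = (1 - p) x 3 + p x 18, since an equal rate cancels: 9.0, 12.0 and 15.0 ppm for p = 0.4, 0.6 and 0.8.

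CM = [(1 - p) x 0.85 x 3 + p x s x 18] / [(1 - p) x 0.85 + p x s].

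Example, p = 0.6 and s = 0.5: (1.02 + 5.40) / (0.34 + 0.30) = 6.42 / 0.64 = 10.03 ppm. False CM benefit = 12.0 - 10.03 = 1.97 ppm.

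False CM benefit (NR minus CM, ppm):

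| p | s = 0.7 | s = 0.5 | s = 0.3 |
|---|---|---|---|
| 0.4 | 0.68 | 1.78 | 3.14 |
| 0.6 | 0.71 | 1.97 | 3.81 |
| 0.8 | 0.49 | 1.47 | 3.22 |

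At s = 0.8 the benefit is about 0.2 ppm. If CM sends smoking and abstinent samples at the same rate, it is zero.

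**Step 2, would week-level imputation repair this?** In the worst cell (p = 0.8, s = 0.3) CM sends 0.2 x 0.85 + 0.8 x 0.3 = 0.41 of its samples. With independent samples, a week is empty with probability 0.59^14 = 0.0006. Clustering would raise this, but a rule that acts only on empty weeks cannot repair partly filled ones.

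**Step 3, baseline B for each unsent sample before averaging.**

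NR = 0.8 x (NR mean) + 0.2 x B.

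CM = (1 - p) x 0.85 x 3 + p x s x 18 + [1 - (1 - p) x 0.85 - p x s] x B.

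False CM benefit with B = 20 (negative means against CM):

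| p | s = 0.7 | s = 0.5 | s = 0.3 |
|---|---|---|---|
| 0.4 | 0.43 | 0.27 | 0.11 |
| 0.6 | 0.22 | -0.02 | -0.26 |
| 0.8 | 0.01 | -0.31 | -0.63 |

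The range is -0.6 to +0.4 ppm. With a higher baseline the worst cell (p = 0.8, s = 0.3) overcorrects. At B = 25, NR is 17.0 and CM is 0.51 + 4.32 + 0.59 x 25 = 19.58, a difference of -2.6 ppm. At B = 30, NR is 18.0 and CM is 22.53, a difference of -4.5 ppm.

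**Step 4, share of scheduled samples that are abstinent, unsent counted as not abstinent.** NR = (1 - p) x 0.80 and CM = (1 - p) x 0.85. The rate s does not appear, so withholding smoking samples cannot move it. The residual is 0.05 x (1 - p) = 3, 2 or 1 percentage points, which comes from the assumed 85% against 80%.

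**Scale as an effect size.** A separate simulation used other assumptions: 16 per arm, 4 weeks of 14 videos, 3 and 20 ppm, 25% of samples abstinent, 90% submission otherwise, identical smoking, and a two-sided t-test on each person's mean as a stand-in for the model. Filling only empty weeks, it gave a spurious d of -0.18 or -0.36, and p at or below .05 in 8% or 17% of trials, when CM sent 50% or 30% of smoking samples. With each unsent video imputed, the bias was about zero. These d values depend on the spread between participants that was simulated.

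**The case against.** The imputation sentence names no unit. If it is meant for each video before averaging, most of the bias goes, as Step 3 shows, so a reader who infers that imputation can never reach the unsent samples goes beyond the text. That stands: the documents do not settle the unit. But the averaging sentence comes first and the model works by session, so filling only empty weeks is the natural reading, and an analyst following the plan could well adopt it.

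A reader might also infer that VAR + mCM *will* look better. The documents do not support that. All arms are asked to send videos twice a day, no submission rates are given, and the lack of a voucher is only a financial reason to withhold. The bias is conditional on differential submission.

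Nor is CO designated the lead R33 measure. R33 Aim 1 names it together with cigarettes per day, and the outcome list places expired CO among the secondary variables.

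Finally, part of the remedy is already planned: the total of abstinent samples is among the analysed outcomes and is not inflated by withholding. This narrows the point but does not remove it, because mean CO is still analysed and would still yield an effect size.

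**Conclusion.** The point holds in conditional form. The payment rule ties submission to arm and CO value, and the plan, read in the order written, leaves unsent samples out of the weekly mean. If VAR + mCM participants withhold smoking samples, mean CO can favour that arm by about 0.5-0.7, 1.5-2.0 or 3.1-3.8 ppm with identical smoking, at 70%, 50% or 30% submission of those samples. Every rate and CO level behind these figures is an assumption.

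The scope is limited to VAR + mCM against the NR arms, mean CO, Weeks 2-5. Week 1 pays all arms alike, and VAR + NR against PLA + NR has no differential incentive. Cotinine and cigarettes per day do not depend, as described, on which videos arrive. The abstinent-sample total is not inflated by withholding; the consecutive count is safe too, provided an unsent sample breaks the run. It would therefore be wrong to conclude that the R33 smoking results as a whole are biased.

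**What to change.** 1. State that baseline CO is imputed for each unsent scheduled sample (14 a week) before the weekly mean is taken, in all three arms.
2. Add sensitivity analyses, including the mean of submitted samples only, because per-sample imputation can overcorrect when baseline exceeds current smoking CO.
3. For the video-based VAR + mCM versus NR comparison, rely mainly on the planned total of abstinent samples, expressed as a share of scheduled samples with unsent counted as not abstinent. State also that an unsent sample ends a consecutive run.
4. Report the submission rate by arm and week.

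The cost is a few sentences in the analysis plan and some data handling; no new data are needed. There are two downsides. Imputation may work against VAR + mCM (up to about 4.5 ppm at a 30 ppm baseline in the worst case above). The share still favours an arm that sends more of its abstinent samples (1 to 3 percentage points under these assumptions).

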A total of 48 randomized participants are planned for the R33 phase. With 20% attrition estimated between enrollment and randomization, we anticipate needing to enroll up to 60 participants (20 per group) to include 48 in the intent-to-treat sample. Given that the PAR-14-230 funding announcement indicates that Stage 1B pilot studies funded through this R33 mechanism “are not expected to have sufficient power to conduct a strong test of efficacy”, we have not attempted to power this study to detect significant differences among the groups. We will focus on determining the feasibility and initial efficacy (i.e., effect sizes) of this intervention to determine if a larger-scale trial is warranted.

Trial Management

List of Participating Sites:

Brown University

Projected Timetable

Recruitment (cumulative)

R21 phase:

Year 1: 24 participants

Year 2: 48 participants

R33 phase:

Year 3: 16 participants

Year 4: 32 participants

Year 5: 48 participants

Target Population Distribution (e.g., women, minorities, etc.)

Age Range: Participants will be 18-65 years of age. Those under 18 will be excluded because the efficacy and safety of VAR in children has not been established.

Gender: Both men and women will be included. About 60% male participants are anticipated because schizophrenia is more prevalent among men (Aleman et al., 2003).

Racial and ethnic groups: Ethnicity/race will not be a selection/exclusion factor for study participation. Based on census data and our recent studies, we anticipate that 75% of participants will be Caucasian, 20% African American or multiracial, 4% Asian, 1% Native American and 15% Hispanic.

Data Management and Analysis

Data Entry, Acquisition and Transmission

Data will be entered directly by the participant or by the Research Assistant. Research materials include paper or computer-administered (Qualtrics or REDCap) questionnaires and tasks, structured clinical interviews, videos of participants providing a breath CO sample, breath samples for analyzing carbon monoxide and alcohol levels, saliva samples for analyzing cotinine, and urine samples for assessing tobacco toxicity biomarkers, illicit drug use and pregnancy.

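### For R33 outcomes other than cognition the role of the pre-treatment value is not specified; stating it as a covariate would sharpen the effect sizes at almost no cost

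*Combined protocol and SAP*

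**What the plan says.** Data Analysis Plan, R33 phase, puts all dependent measures into generalized linear mixed models with Group between subjects and Session within subjects, and will examine main effects and the Group x Session interaction. In the list of measures only one entry carries a baseline instruction: "cognitive scores (baseline co-varied". The paragraph adds that the approach controls for person-level covariates, but lists none. It does not say whether the pre-treatment session is a level of Session.

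Pre-treatment values exist. The same paragraph states "Baseline data will be imputed for missing". The R33 description in the Summary of the Protocol has cotinine, quit interest and the cognitive battery collected at the beginning and end of the intervention, and smoking, craving, withdrawal, mood, subjective effects and psychiatric symptoms assessed weekly. It refers to a Session 6 for a 5-week treatment, so Session 1 is probably the baseline visit (an inference). Trial Safety, risk item 6, places the movement scales at screening and the last session.

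Power Calculation and Sample Size, R33 phase, gives the purpose: "We will focus on determining the feasibility and initial efficacy (i.e., effect sizes) of this intervention".

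**The concern.** The phase is meant to deliver effect sizes from three small arms. When the role of baseline is left open, at least three analyses fit the text: post-baseline values alone, baseline as one more level of Session, or baseline as a covariate. They give different estimates and different precision, and the choice could be made after the data are seen. Two of the three cost something:

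- If baseline is unused, stable differences between people in smoking and craving add to the error of the Group comparison.
- If baseline is an unconstrained Session level, the Group main effect averages in a time point at which treatment cannot yet have acted. The interaction escapes that dilution, but is less precise than a covariate-adjusted contrast.

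Cotinine shows the gap most clearly. It is on the same beginning-and-end schedule as the cognitive battery, yet only the cognitive scores have their baseline covaried.

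**Working it through.** **The plan's own figure.** "A total of 48 randomized participants are planned for the R33 phase". Allowing for 20% attrition before randomization, 48 / (1 − 0.20) = 60, or 20 per group enrolled, as stated. Randomized per arm: 48 / 3 = 16, assuming equal allocation. The section states no R33 power or precision: "we have not attempted to power this study to detect significant differences among the groups".

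**What the text allows.** The R21 analysis does not settle the R33 reading, because it handles baseline in different ways. QSU and MNWS are modelled over Sessions 2–8, without the Session 1 baseline. CEQ uses Sessions 1 and 8 as two levels of a factor. Psychiatric scores include Screening as a level of Time. For R33 outcomes measured only twice (cotinine, quit interest, movement scales), a model with Session as a factor and no baseline covariate must take baseline as one of its two levels.

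**Dilution of the Group main effect if baseline is an unconstrained Session level.** A constant effect δ at m post-baseline sessions, averaged with zero at baseline, becomes δ × m/(m + 1):

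- m = 4 (Weeks 2–5): 4/5 of δ
- m = 5: 5/6 of δ
- m = 1 (beginning and end only): 1/2 of δ

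**Precision.** Assumptions: continuous outcome, SD 1 at each session, compound symmetry with correlation r, complete data, n = 16 per arm. The plan gives no correlation, so r = .3, .5 and .7 are assumed. Let P = (1 + (m − 1)r)/m, the variance of a person's mean over m post-baseline sessions. The variance of a two-arm difference is:

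- unadjusted: (2/n) × P
- change from baseline, as in an unconstrained Group x Session contrast: (2/n) × (P + 1 − 2r)
- baseline as covariate: (2/n) × (P − r²) × (1 + 1/43), the last factor being the small-sample cost of one covariate with three arms of 16

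Worked case, m = 4, r = .3: P = (1 + 0.9)/4 = 0.475.

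- Unadjusted: √(0.125 × 0.475) = 0.244
- Change: √(0.125 × 0.875) = 0.331
- Covariate: √(0.125 × 0.385 × 1.0233) = 0.222

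| m = 4 | r = .3 | r = .5 | r = .7 |
|---|---|---|---|
| SE unadjusted | 0.244 | 0.280 | 0.311 |
| SE change | 0.331 | 0.280 | 0.217 |
| SE covariate | 0.222 | 0.219 | 0.191 |
| Cut in SE vs unadjusted | 9% | 22% | 39% |
| Cut in SE vs change | 33% | 22% | 12% |
| 95% half-width, unadjusted | 0.49 | 0.56 | 0.63 |
| 95% half-width, change | 0.67 | 0.56 | 0.44 |
| 95% half-width, covariate | 0.45 | 0.44 | 0.38 |

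A simulation of 20,000 trials at each r agreed with these standard errors to within about 0.003.

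**Single post-baseline score (m = 1).** At r = .3 the SE goes from 0.354 unadjusted to 0.341 with the covariate. That is a cut of between 3% and 4%, or just under 5% if the cost of the covariate is ignored (√(1 − .09) = 0.954). At r = .5 it goes from 0.354 to 0.310 (12%), and at r = .7 from 0.354 to 0.255 (28%).

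**The case against.** A reader might infer that the plan leaves the collected baselines out. The text does not establish that. They may be the first level of Session, and six sessions for five weeks makes that plausible. They may also be among the person-level covariates, in which case there is no loss. What the text supports is that their role is unspecified.

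A reader might also infer that chance baseline differences bias the R33 comparisons. Under randomization an unadjusted comparison is unbiased, so the loss is one of precision. If baseline is a Session level, the Group x Session interaction is already referenced to it, and stable between-person differences cancel there. This part of the objection stands. What remains is that an unconstrained change contrast is less precise than the covariate at every correlation assumed here, and that the plan also examines the Group main effect, which would be diluted.

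Power gains are a poor way to state the size of the problem. The plan disclaims power for R33, and a calculation that sets one post score against an unadjusted comparator ignores both the repeated sessions and the change-type analysis the plan may intend. The formulas also do not carry over directly to non-linear models, such as those for counts of abstinent samples or for Stage of Change.

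**Conclusion.** The concern holds as a specification gap with a probable loss of precision. No figure in the R33 section is wrong and no bias follows. Baseline adjustment is specified for cognition alone, although pre-treatment values of other outcomes are available. Whether baseline is unused or an unconstrained Session level, the covariate gives the smaller standard error over the whole assumed range. With four post-baseline sessions the cut is about 9% to 39% against unadjusted and 12% to 33% against change. If baseline is a Session level, the Group main effect also shrinks to 4/5 or 5/6 for a constant effect on weekly measures, and an end effect is halved for measures taken only twice.

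The size depends on correlations the documents do not give, on compound symmetry and on continuous outcomes. It can be small: 3–5% for one post score at r = .3. It is zero if the unnamed covariates already include each outcome's baseline. Because effect sizes are a stated product of the phase and the remedy is nearly free, the change should be made.

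**What to change.** In Data Analysis Plan, R33 phase:

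- For each repeated outcome with a pre-treatment value (cigarettes per day, CO, QSU, MNWS, mood, CEQ, psychiatric scales), enter the participant's pre-medication value of the same measure as a covariate, with only post-baseline sessions as levels of Session. Equivalently, keep baseline as a Session level with group means constrained equal there.
- For outcomes measured only at beginning and end (cotinine, Stage of Change and Contemplation Ladder where so scheduled, movement scales), compare the end value between groups adjusted for baseline, without a Session factor.
- For weekly video CO, use the laboratory CO from screening or Session 1, since Week 1 videos fall in the medication run-up. Total and consecutive abstinent samples have no baseline of their own; use baseline CO or cigarettes per day.
- List the person-level covariates and define the levels of Session.
- Take the reported effect sizes from the adjusted contrasts, standardised by a raw rather than a residual SD, and state which. The residual SD shrinks with adjustment: for a single score at r = .5 it is √(1 − .25) = 0.87 of the raw SD, so d would read about 15% larger (1/0.87 = 1.15). The baseline SD of smoking measures needs caution, because entry requires at least 10 cigarettes per day and CO above 10 ppm, which truncates the spread.

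The cost is a short paragraph, one degree of freedom per model and no new data.
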